5.1.3 Relative Vaccine Effectiveness Estimate by Vaccine type

We have an *a priori* interest in evaluating relative vaccine effectiveness by vaccine type regardless of whether the overall relative vaccine effectiveness differs significantly between either cell-culture based influenza vaccine and egg-based influenza vaccine. Vaccine types include:

- 1. A/H1N1
- 2. A/H3N2
- 3. B/Victoria
- 4. B/Yamagata

Relative vaccine effectiveness comparing cell-culture based influenza vaccine and egg-based influenza vaccine and recombinant HA influenza vaccine and egg-based influenza vaccine will be estimated for each vaccine type.

5.1.4 Power of the study for the primary endpoint

The sample size estimates for this study were based on a power of 0.80 a onesided alpha of 0.25, and an assumed incidence of five per hundred among the eggbased vaccination group to detect a relative vaccine effectiveness of at least 30%.

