9.3.3 Scientific Merit

We propose to conduct a prospective study to compare immune responses and effectiveness of immunization to prevent influenza acquisition in DEERS-eligible adults (≥18 years and older) receiving egg-based, cell-culture-based, or recombinant inactivated influenza vaccines. This study will be conducted at selected military treatment facilities in a well-described military population comprised of individuals with both high (active duty personnel) and moderate (military retirees/beneficiaries) vaccination coverage. The study results would provide new and important information on the immune responses and vaccine effectiveness by vaccine formulation. Publication in a high impact journal is likely as this information may have important influenza vaccination policy implications for both the military and the US population at large. The immunogenicity data may inform the development of effective universal influenza vaccines.

9.4

Objectives/Specific Aims/Research Questions:

Describe the purpose and objective(s) of the study, specific aims, and/or research questions /hypotheses

Primary Aim:

Specific Aim #1: Comparison of the relative effectiveness (prevention of laboratory-confirmed influenza illness) of three types of licensed seasonal influenza vaccines.

Research Question: Is either the cell-culture based vaccine or the recombinant vaccine more effective than egg-based vaccine?

There are two hypotheses of interest based on influenza attack rates (AR):

Assuming relative VE of 30% => $1 - AR_1/AR_{eqg} = 0.3$

Therefore 1- 0.3 = AR_1/AR_{egg} = RR therefore 0.7= AR_1/AR_{egg} =RR (AR_1 =attack rate in either cellculture based or recombinant vaccine)

Ho: RR=1 vs HA: RR< 1; p=0.025; The RR to be tested is defined as: 1) RR1=ARcell / ARegg and 2) RR2=ARrecombinant / ARegg

Endpoint:

Influenza attack rates in the egg-based, cell-culture-based, and recombinant protein influenza vaccines arms of the study in the 2018-2019, 2019-2020, 2020-2021, and 2021-2022 seasons.

Secondary Aim

Specific Aim #2: (Immunogenicity substudy) Determine whether cell-culture-based, egg-based and recombinant influenza vaccines give comparable HI and PVN titers to egg- and cell-matched vaccine antigens. An outcome of this objective is the potential to determine whether cell-culturebased vaccine antigens can provide broader coverage of circulating viruses than egg-based vaccine antigens.

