The ability of the study to detect a difference in effect is proportionate to the incidence of the outcome. A total of 172 influenza cases were reported among the 10,771 subjects enrolled in first three years of the study (2018-2021). The influenza attack rate has ranged from 0% in third season (COVID-19 pandemic), to 2.5% in the second season, with an overall attack rate 1.6% The observed attack rates are lower than baseline attack rates of 5% and 3% that formed the basis of sample size calculations for the first three years of the study. Consequently, the power to detect significant differences in VE between vaccine arms has been too low to due to the low attack rates. For the fourth year of the study is to increase the enrollment target from 15,000 to 18,00 to enhance power to detect significant differences in VE between attack rates are lower.

Secondary Aims:

Specific Aim #2:

Determine whether cell-culture-based and egg-based influenza vaccines give comparable HI and PVN titers to egg- and cell-matched vaccine antigens. An outcome of this objective is the potential to determine whether cell-culture-based vaccine antigens can provide broader coverage of circulating viruses than egg-based vaccine antigens.

Research Question: Is the proportion of subjects who seroconvert in either the cell-culture based or recombinant vaccine arm of the study greater than in the egg-based vaccine arm of the study.

There are two hypotheses of interest for Specific Aim 2, based on the seroconversion rates (SCR)

H₀: RR=1 vs H_A: RR < 1; p=0.025; The RR to be tested is defined as: 1) RR1=SCRcell / SCRegg and 2) RR2=SCRrecombinant / SCRegg

1. Endpoints:

- Humoral responses: HAI titer, anti-NA titer, virus-neutralizing titer
- Cellular responses (exploratory): frequency of antigen-specific CD4 and CD8 cells, B cells

SA 2.1: To obtain post-vaccination sera panels to determine breadth of reactivity to circulating strains.

This will be accomplished by recruiting consenting adults to an IRB-approved study conducted during a routine influenza vaccination campaign, collecting sera up to 30 days before and 21-35 days after vaccination with egg- or cell-culture-based or recombinant influenza vaccines. The samples will be de-identified and shipped to partner laboratories for aliquoting, storage, and antigenic analyses. We intend the study to be conducted during early vaccination campaigns performed at DoD facilities.

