11.5 Please provide a justification for your sample size

Main Study

Based on an alpha of 0.025 (1-sided) and a power of 0.80, a sample size of 18,000 (6,000 per arm) subjects has the power to detect a 33% difference in effectiveness between egg-based vaccine and two other vaccine preparations, assuming an influenza incidence of 2.3% in the egg-based arm and 1.54% in the cell-culture-based and recombinant arms. It assumes that 15% of subjects will be lost to follow-up.

Substudy

Based on an alpha of 0.025 (1-sided) and a power of 0.80, a sample size of 1,200 subjects (400/arm) has the power to detect a 22% relative difference in seroconversion rate if there is a 50% seroconversion at day 28 among the egg-based vaccine recipients. It assumes that 15-20% of subjects will be lost to follow-up.

11.6 Data Analysis Plan:

See section 11.1

12.0

Participant Information

12.1 Subject Population:

The study is comprised of DEERS-eligible adults (active duty, retirees and beneficiaries) vaccinated (at an MTF) (will be vaccinated) with one of the licensed egg-based, cell-culture-based or recombinant influenza vaccines during the 2018-2019, 2019-2020, 2020-2021, 2021-2022 influenza seasons in the United States. Subjects enrolled in the study during 2018-2019, 2019-2020, and/or 2020-2021 may also be enrolled in the 2021-2022 season.

12.2 Age Range:

Check all the boxes that apply. if the age range of potential subjects (specimens, records) does not match the range(s) selected, please specify in the text box.

0-17

- ✓ 18-24
- 25-34
- 35-44
- 45-54
- 55-64
- 65-74
- 75+

12.3 Gender:

- Male
- ✓ Female
- C Other

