3.2 Immunogenicity Sub-Study

Nested within this trial is an immunogenicity sub-study, in which 1,000 subjects will have their blood drawn prior to influenza vaccination and again at 21-35 days post-vaccination to assess changes in immune responses to the vaccines. Collection of a buccal swab for host genomic studies will be optional at enrollment or the 21-35 days post-vaccination visit.

	Recruits	Non-recruits	Non-recruits; Sub-Study
Consent and sociodemographic data collection	X	Х	Х
Sub-Study blood draw (pre-vaccination)			X
Vaccination with one of 3 vaccines	X	Х	Х
Weekly surveillance begins for non-recruits 14 days after vaccination		X	X
Sub-Study blood draw (post-vaccination)			X
ILIs - Visit 1 (if ILI is experienced) - nasopharyngeal swab, blood sample	X	X	X
ILI severity survey (if ILI is experienced)		Х	X
ILIs - Visit 2 (if ILI is experienced) - blood sample ~28d after Visit 1		X	X

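### SAP 5.1.4 states the primary power on a one-sided alpha of 0.25, a 5% egg-arm attack rate and a 30% effect, none of which belongs to the 18,000-subject design

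*SAP*

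**What the plan says.** SAP 5.1.4 is headed as the power of the study for the primary endpoint. It says the sample size rests on "a power of 0.80 a onesided alpha of 0.25, and an assumed incidence of five per hundred among the eggbased vaccination group", in order "to detect a relative vaccine effectiveness of at least 30" percent. It gives no number of subjects and no allowance for loss to follow-up.

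The rest of the plan differs:

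- **Test level.** SAP 5.1.2 declares significance at a one-sided p-value of 0.025. Protocol 9.4, 11.1 and 11.5 use the same level.
- **Size.** SAP 3.1 describes four seasons and 18,000 subjects, about 6,000 per arm.
- **Attack rate.** Protocol 11.5 justifies the 18,000 by "assuming an influenza incidence of 2.3% in the egg-based arm and 1.54% in the cell-culture-based and recombinant arms", with 15% lost to follow-up. Protocol 11.1 reports 172 cases in 10,771 subjects over three seasons and says: "The observed attack rates are lower than baseline attack rates of 5% and 3% that formed the basis of sample size calculations".
- **Effect.** Protocol 11.1 and 11.5 use 33%. Protocol 9.4 still has "Assuming relative VE of 30" percent, and SAP 6.1 also refers to 30%.
- **Sub-study.** SAP 3.2 describes a sub-study "in which 1,000 subjects will have their blood drawn prior to influenza vaccination". Protocol 11.5 makes its sub-study power claim for 1,200 (400 per arm).

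**The concern.** Alpha, attack rate and effect size in SAP 5.1.4 all disagree with the design the SAP otherwise describes. The printed alpha is ten times the level at which the test will be run. A reader of the SAP alone would conclude that the trial has 80% power for a 30% RVE.

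That matters most if the result is null. Protocol 9.7 and 14.4 say that minimal differences between vaccines would support leaving current recommendations as they are. A null finding read against a claim of 80% power for 30% would carry more weight than the design can give it.

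**Working it through.** **Method.** Two-proportion normal approximation, 1:1, one-sided, no continuity correction:

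n per arm = [z(1−α)·√(2p̄(1−p̄)) + z(0.80)·√(p₁(1−p₁)+p₂(1−p₂))]² / (p₁−p₂)²

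Loss of 15% is allowed for by dividing by 0.85; 6,000 × 0.85 = 5,100 evaluable per arm.

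**1. Protocol 11.5 (2.3% vs 1.54%, α = 0.025).** The first root is 0.19407 and the second 0.19399.
- n = (1.960 × 0.19407 + 0.8416 × 0.19399)² / 0.0076² = 5,117 per arm; /0.85 = 6,020; × 3 = 18,060. The stated figure is 18,000.
- Power at 5,100: Φ[(0.0076 × √5,100 − 1.960 × 0.19407)/0.19399] = Φ(0.837) = 79.9%. The protocol's figure reproduces.

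**2. SAP 5.1.4 as printed (5% vs 3.5%, α = 0.25).** The roots are 0.28528 and 0.28509.
- n = (0.6745 × 0.28528 + 0.8416 × 0.28509)² / 0.015² = 831 per arm; 978 with 15% loss; 2,934 in total.
- At 6,000 per arm the power is 99.97%.

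**3. SAP 5.1.4 with only the alpha corrected (α = 0.025).**
- n = (1.960 × 0.28528 + 0.8416 × 0.28509)² / 0.015² = 2,838 per arm; 3,339 with 15% loss; 10,017 in total.
- Power is 96.4% at 5,100 per arm and 98.3% at 6,000.

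Neither version of the SAP inputs leads to 18,000 subjects or to 80% power at that size.

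**4. Power for the 30% effect at the protocol's attack rate (2.3% vs 1.61%, α = 0.025).**
- At 5,100: Φ[(0.0069 × √5,100 − 1.960 × 0.19579)/0.19573] = Φ(0.557) = 71.1%. At 6,000: 77.9%.
- 80% needs 6,319 per arm, or about 22,300 in total with 15% loss.

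**5. Sensitivity to the attack rate, 30% effect assumed in both new arms.** The fourth-season rate is not in the documents, so both cases below are assumptions.

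| Assumed overall attack rate | Implied egg-arm rate | Power at 5,100 | Power at 6,000 |
|---|---|---|---|
| 1.6% (172/10,771, carried forward) | 3 × 1.6% / 2.4 = 2.0% | 65% | 72% |
| 1.96% (remaining 7,229 subjects at season 2's 2.5%: (172 + 180.7)/18,000) | 3 × 1.96% / 2.4 = 2.45% | 74% | 80% |

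**6. Sub-study (50% vs 50% × 1.22 = 61%, α = 0.025).**
- 400 per arm less 20% or 15% loss leaves 320 or 340: power 80% or 82%.
- 1,000/3 = 333 per arm less the same loss leaves 267 or 283: power 73% or 75%.

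**The case against.** Four points can be made for the plan.

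- **The 0.25 is very likely a dropped zero.** Every other place uses 0.025 and no analysis uses 0.25. This stands, and the 2,934 figure describes no design anyone intended. But restoring the zero leaves inputs that give about 10,000 subjects, so the section is still wrong.
- **The text is in the past tense and gives no N.** Protocol 11.1 confirms that 5% was an earlier planning rate. As history this is fair. But the section is headed as the power of the study, sits in the four-season SAP, and does not say that it has been superseded.
- **The current sample size is justified in protocol 11.5.** This stands: the 33% calculation reproduces, and no defect in the enrolment target is shown. What lacks support is 80% power for 30%.
- **The observed 1.6% is a pessimistic guide.** It includes a season with no influenza. This stands too. With a fourth season at 2.5%, power for 33% would be 83% at 5,100 per arm, and power for 30% would reach 80% if nobody were lost. The 1.6% scenario is therefore only one end of a range, and the conclusion does not need it.

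The sub-study mismatch concerns a different endpoint, and SAP 3.2 makes no power claim of its own. It is included because it is the same failure to keep the two documents aligned on size and power.

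**Conclusion.** The concern holds. All three design inputs in SAP 5.1.4 conflict with the current design, and correcting the alpha alone does not mend it. On protocol 11.5's own attack rate and a one-sided 0.025 test, power is 80% for a 33% effect. For the 30% that SAP 5.1.4 and protocol 9.4 name, it is 71% after 15% loss and 78% with no loss. A sub-study of 1,000 would have about 73–75% power where the protocol claims 80% for 1,200.

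These figures rest on the normal approximation, equal arms and the protocol's loss rates. The type I error of the planned test is unaffected, since SAP 5.1.2 sets it at 0.025.

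**What to change.** - **SAP 5.1.4:** replace the paragraph with the protocol 11.5 basis: one-sided alpha 0.025 per comparison, 2.3% versus 1.54%, 33% RVE, 15% loss, 6,000 per arm, power 80%. Add that power for 30% is about 71% on the same assumptions. If the 5% and 30% are kept as history, label them as the superseded first basis and correct the alpha.
- **Effect size:** use one target in protocol 9.4, 11.1 and 11.5 and in SAP 5.1.4 and 6.1. Only 33% matches 18,000, and protocol 11.1 states it as the effect wanted. If the sponsor prefers 30%, the stated power must fall accordingly.
- **Sub-study:** set SAP 3.2 to 1,200 (400 per arm), or keep 1,000 and restate the power as about 73–75%.

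The cost is wording in the two documents. No test, dataset or enrolment target changes; the stated power for a 30% effect becomes less favourable.

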5.1.5 Plan for handling missing data and extreme values

Data will come from multiple sources including an enrollment document and from medical records. Care will be taken to minimize missing data, but sometimes this will still occur. For each variable, the data managers will review the data and calculate the percent missing. In addition, extreme values will be

identified. Participants with missing vaccination or outcome data will be excluded. A sensitivity analysis will be performed using only those non-recruit participants with at least 50%/75% of the weekly survey data in order to ensure that findings are consistent.

5.2 Immunogenicity Endpoint (Sub-Study)

5.2.1 Evaluating balance between the three treatment arms

Randomization is used to control for, or reduce, selection bias among study participants. Randomization should control for both measured and unmeasured confounders/covariates as well as both known and unknown confounders/covariates and background characteristics.

Comparison between groups will occur at the interim analysis at the end of the first influenza season and at the end of the study.

We will compare among the subset the three vaccination groups for basic background characteristics and known measured confounders (See Appendix *X*).

5.2.2 Endpoints

5.2.2.1 Relative risk for seroconversion

Relative risk of seroconversion among participants who received cellculture-based influenza vaccine (FlucelvaxR) as compared to those receiving egg-based influenza vaccine will be calculated using the following formula:

$$RR_{cell} = \frac{p_{cell}}{p_{egg}}$$

Where:

 p_{cell} = proportion seroconvert among the cell-culture-based influenza vaccination group

 p_{egg} = proportion seroconvert among the egg-based influenza vaccination group

and

Relative risk of seroconversion among participants who received recombinant HA (FluBlokR) influenza vaccine as compared to those receiving egg-based influenza vaccine will be calculated using the following formula:

$$RR_{recombinant} = \frac{p_{recombinant}}{p_{egg}}$$

Where:

 $p_{recombinant}$ = proportion seroconvert among the recombinant HA influenza vaccination group

 p_{egg} = proportion seroconvert among the egg-based influenza vaccination group

The proportion that seroconvert equals the number seroconvert (definition 3.1.2.3) divided by the number of vaccinated individuals that were enrolled in the Sub-Study and had the pre- and post-blood draws.

Confidence intervals (95%) will be calculated using the standard formulas for relative risk. The relative risk will be statistically significant if the p-value is less than or equal to 0.025 (one-sided test). The interim analysis for relative risk after the first influenza season uses a stricter p-value (<0.0001). Because of this, the final analysis will not need to adjust the p-value out of concerns about multiple looks.

Relative risk for seroconversion as defined in 5.2.2.1 will be evaluated for each vaccine-type (A/H1N1, B/Yamagata, B/Victoria, and A/H3N2);

5.2.2.2 Geometric Mean Titers (GMTs) – GMTs will be calculated pre- and post-vaccination. Non-inferiority will be based on a 2-sided test comparing post-vaccination GMTs between vaccine types.

5.2.2.3 Mean-Fold Rise – Ratios of participant post-vaccination titers divided by the pre-vaccination titers.

5.3 Other

5.3.1 Influenza-confirmed hospitalization – Relative risk of laboratory confirmed influenza hospitalization in cell-culture-based vaccine recipients compared with egg-based vaccine recipients (and comparing recombinant vaccine with egg-based vaccine)5.3.2 Influenza-like illness - Relative risk of laboratory confirmed influenza hospitalization in cell-culture-based vaccine recipients compared with egg-based vaccine recipients (and comparing recombinant vaccine with egg-based vaccine recipients compared with egg-based vaccine recipients (and comparing recombinant vaccine with egg-based vaccine vaccine with egg-based vaccine)

5.3.3 Work days lost to influenza and ILI – Compare mean work days lost to influenza and ILI between vaccines using t-tests and/or multivariate linear models.

5.3.4 Healthcare costs/utilization for influenza and ILI - TBD.

6. Interim Analysis after first influenza season (2018/19)

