propose to include the HAs of at least 6-10 recent virus isolates per subtype/lineage. PVN titers against recent virus isolates that are >4 fold different from the homologous vaccine antigen will be considered low reactors (LRs). The breadth of reactivity will be scored by calculating the number of LRs identified for each study subject, e.g., sera that react to all antigens will be given a score of 100%, sera that react to no antigens will be given a score of 0% and sera that react to 4 of 10 antigens will be given a score of 40%. The overall breadth of reactivity for each study Arm will be calculated as the average breadth of reactivity for all persons in the Arm. If the difference between the groups is not significant, additional antigens within the subtype/lineage but that are known to be antigenically-distinct, may be tested.

SA 2.5: To examine the breadth of reactivity against past strains.

Recent studies demonstrate a back-boost effect following vaccination, i.e. increased antibody titers against influenza antigens from past vaccines or infections. The human immune responses are therefore impacted by prior vaccination history or infection. To retain the possibility of performing additional tests that examine the back-boost effect, left over sera will be stored for future additional investigations of how pre-existing breadth of antibody reactivity to past influenza strains influences responses to current influenza vaccines.

Exploratory Aims:

Specific Aim #3: To determine if the impact of the influenza vaccine on disease burden and the attributable healthcare costs differs by product type.

An analysis of the impact of ILI and SARI on health care utilization will allow a more detailed estimation of the burden of infections caused by these pathogens in military populations. The collection and analysis of health care utilization information will be useful for informing priorities for ARI control and will serve as a basis for the comparison of the effectiveness of different ILI control measures to enhance Force Health Protection.

Endpoints:

- Incidence of PCR-confirmed influenza cases
- Frequency of influenza-confirmed hospitalization
- Frequency of influenza-like illness
- Work days lost due to influenza
- Work days lost due to influenza-like illness
- · Healthcare costs/utilization attributable to influenza
- · Healthcare cost/utilization attributable to influenza-like illness

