2.3 Exploratory Objectives

Compare the disease burden associated with receiving cell-culture-based (FlucelvaxR) and recombinant HA (FluBlokR) influenza vaccines to egg-based influenza vaccines.

Relative risk of laboratory-confirmed influenza hospitalization Relative risk of ILI Mean workdays lost due to laboratory-confirmed influenza Mean workdays lost due to ILI

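### SAP 5.3.2 names influenza hospitalisation as the outcome under its ILI heading, so SAP section 5 has no correct analysis line for ILI occurrence

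*SAP*

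**What the plan says.** SAP 2.3 sets the exploratory objective: "Compare the disease burden associated with receiving cell-culture-based (FlucelvaxR) and recombinant HA (FluBlokR) influenza vaccines to egg-based influenza vaccines". It then lists four measures. Hospitalisation with confirmed influenza is one and "Relative risk of ILI" is another; the other two are work days lost, including "Mean workdays lost due to ILI".

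SAP 4.1.3.1 and 4.1.3.2 define influenza hospitalisation and ILI as two different endpoints.

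SAP 5.3 then gives the analyses:

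- 5.3.1, hospitalisation: "Relative risk of laboratory confirmed influenza hospitalization in cell-culture-based vaccine recipients compared with egg-based vaccine recipients", with the matching recombinant comparison.
- 5.3.2, ILI: "Influenza-like illness - Relative risk of laboratory confirmed influenza hospitalization in cell-culture-based vaccine recipients compared with egg-based vaccine recipients", again followed by the recombinant comparison.
- 5.3.3, work days lost: "Compare mean work days lost to influenza and ILI between vaccines using t-tests and/or multivariate linear models".
- 5.3.4, costs: "Healthcare costs/utilization for influenza and ILI - TBD".

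Protocol 11.1, Specific Aim 3, lists "Frequency of influenza-like illness" among the exploratory endpoints without a method, and protocol 11.6 only refers back to 11.1.

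**The concern.** Section 5.3 is the operative methods text, the part a programmer follows. Under the ILI heading it asks for the hospitalisation outcome a second time. The listed ILI comparison then either goes unreported or is analysed by rules chosen after the data are available.

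Those rules are not trivial here. SAP 3.1 follows participants through repeated ILI episodes at least 30 days apart, so episodes and participants give different counts. Protocol 12.1 lets people enrolled in earlier seasons enrol again in 2021-2022. Recruits receive no weekly survey and are found only when they present at a clinic. Each of these needs a stated convention, and 5.3.2 is where it should be.

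**Working it through.** **Text check.** The claim depends on no power, alpha or event-count calculation, so the main check is to set the entries side by side.

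| Item | Measure named in SAP 2.3 | Endpoint definition | Line in SAP 5.3 |
|---|---|---|---|
| Influenza hospitalisation | Yes | 4.1.3.1 | 5.3.1, matches |
| ILI occurrence | Yes | 4.1.3.2 | 5.3.2, names hospitalisation instead |
| Work days lost, influenza and ILI | Yes | None given in 4.1.3 | 5.3.3, method stated |
| Costs and utilisation, influenza and ILI | Not listed in 2.3 | None given in 4.1.3 | 5.3.4, still to be determined |

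Only the ILI occurrence row has a methods line that contradicts its own heading and objective.

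**Can the gap be filled from elsewhere?** In part. SAP 2.3 supplies the measure (a relative risk) and the comparisons (each non-egg vaccine against egg). It gives no counting rule or denominator. The incidence formula in SAP 5.1.2 is written for laboratory-confirmed influenza only. The protocol gives the endpoint and no method.

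**Which ILI?** SAP 4.1.3.2 requires three symptom groups together: fever or chills, cough or sore throat, and aches or fatigue. Protocol 9.4 (Aim 3) and 10.1 require two: cough or sore throat, plus either feverishness/chills or aches/fatigue. The SAP definition is stricter, so correcting the outcome word alone would leave the endpoint ambiguous.

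**Scale.** Inputs are from protocol 11.5 (6,000 per arm, 15% loss, incidence 2.3% with egg and 1.54% in each other arm) and protocol 11.1 (30 to 40% expected to develop ILI).

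- Followed per arm: 6,000 x 0.85 = 5,100; in total 3 x 5,100 = 15,300.
- Planned influenza cases: 5,100 x (0.023 + 2 x 0.0154) = 5,100 x 0.0538 = 274.
- Participants with ILI: 15,300 x 0.30 = 4,590 to 15,300 x 0.40 = 6,120.
- Ratio: 4,590 / 274 = 17 to 6,120 / 274 = 22.

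The 30 to 40% is an advance projection. If it was made under the protocol's two-group definition, the count under SAP 4.1.3.2 would be lower by an amount the documents do not give.

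**The case against.** The strongest reply is that this is a copy-and-paste slip whose intent is obvious. The heading still says ILI, the entry directly above carries the same wording, and SAP 2.3 states the intended measure and comparators. The endpoint is exploratory, and nothing confirmatory depends on it. The extracted text of 5.3.2 is also damaged: it runs on from 5.3.1 and its ending repeats phrases.

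Most of this stands as a limit on severity. A slip is the likely cause. The damage is confined to the tail of the entry, however, and the heading and wrong outcome read cleanly; the PDF should be checked before editing. Obvious intent does not supply the counting unit, the handling of recruits or the ILI definition.

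Three stronger readings are tempting, and the documents do not support them.

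- *A reader might infer that the plan has no analysis of ILI at all.* SAP 5.3.3 gives a method for work days lost to ILI, and 5.3.4 lists ILI costs as still to be determined. Only occurrence lacks a correct line.
- *A reader might infer that losing this analysis removes the check on differential reporting in an open-label trial.* An ILI relative risk mixes vaccine effect with reporting and cannot separate them by itself. Neither document gives it that role. SAP 5.1.5 has a separate sensitivity analysis by survey completeness.
- *A reader might infer that the ILI analysis must be stratified by site and season.* That does not follow from a wrong outcome word, and the primary analysis in SAP 5.1.2 states no stratification.

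**Conclusion.** The point holds for ILI occurrence. SAP 5.3.2 is wrong as written: it contradicts SAP 2.3, the separate definitions in SAP 4.1.3 and protocol Aim 3, and it leaves one listed exploratory objective without a correct analysis. It should be corrected, but it does not threaten the trial's main conclusion; the primary endpoint, alpha, sample size and interim rule are unaffected.

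The comparison affected would carry roughly 17 to 22 times as many affected participants as the planned confirmed-influenza comparison. That ratio assumes 15% loss in every arm, the protocol's projected ILI percentage and its planned attack rates. It shows scale only, and the textual finding does not rest on it. The one remaining caveat is to confirm the wording of 5.3.2 in the source PDF.

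**What to change.** After checking the PDF, replace the outcome in SAP 5.3.2 along these lines:

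> Relative risk of at least one ILI episode per participant per season, cell-culture-based versus egg-based and recombinant versus egg-based, with 95% confidence intervals by the relative-risk formulas of section 5.1.2. Results for recruits are shown separately because they have no weekly survey.

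State in the same entry which ILI definition applies, after reconciling SAP 4.1.3.2 with protocol 9.4 and 10.1. The study team has to make that choice; the documents do not settle it.

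The cost is about two sentences in the SAP and one decision on the definition. The fix adds no data collection and leaves the primary analysis as it is. It should be made before ILI is compared by arm, so that the counting rule is not chosen with results in view.
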